Study Protocol and Statistical Analysis Plan

Study Title: Internet-based cognitive behavioral therapy for tinnitus in the United States: A randomized controlled trial protocol

Clinical trial registration: NCT04004260 on 2 July 2019.

Funding: National Institute on Deafness and Communication Disorders (NIDCD) of the National Institute of Health (NIH) under the award number R21DC017214.

Ethical approval: Institutional Review Board at Lamar University, Beaumont, Texas, US (IRB-FY17-209).

Document Date: June 22, 2021

Background: Tinnitus, characterized by the perception of sound in the absence of an external stimulus, is one example of such a condition. Managing tinnitus is notoriously challenging as there is often not a curable medical cause. The intervention with strongest research evidence is cognitive behavioral therapy (CBT) for tinnitus. CBT is psychological intervention addressing unhelpful thought patterns and emotional reactions caused by tinnitus (Andersson, 2002). Despite the evidence base, accessibility to CBT for tinnitus is limited due to a dearth of healthcare providers with the knowledge and expertise to provide CBT to this population (Bhatt et al., 2016; Henry et al., 2019).

To overcome this barrier, an Internet-based CBT for tinnitus (ICBT; Andersson et al. 2002) has been developed. The efficacy of ICBT has been indicated in nine clinical trials across mainland Europe and the UK (for review see Beukes et al., 2019). No clinical trials,

Study Objectives:

- 1. To evaluate the efficacy of audiologist-delivered ICBT in reducing tinnitus distress compared with weekly monitoring of tinnitus in the US.
- 2. To ascertain the efficacy of ICBT in reducing comorbidities associated with tinnitus.
- 3. To assess the stability of ICBT intervention effects 2-months post-intervention.

The hypothesis will be that patients with tinnitus would experience greater reduction of tinnitus distress and comorbidities after receiving ICBT compared to patients receiving weekly monitoring.

Study Design

A prospective two-arm delayed intervention efficacy trial with a 2-month follow-up is planned.

Randomization

Participants will be randomized to the *Experimental Group* and received the ICBT intervention for 8-weeks, or the *Control Group* whose participants will be monitored weekly during this 8-week period. During the first phase the experimental group will completed the intervention. Following this both groups will complete T1 (post-treatment) outcome measures. During the second phase, the control group will receive the same ICBT intervention, after which both groups will complete T2 (2 month follow-up) outcomes. This study design, therefore, provided the opportunity to evaluate the intervention effects in two independent groups at three time points as shown in Figure 1.

Study Population

Study eligibility

Inclusion criteria:

- Adults, aged 18 years and over, living in Texas in the US;
- The ability to read and type in English or Spanish;
- Access to a computer, the internet and able to email;
- Experiencing tinnitus for a minimum period of three months and
- A tinnitus severity score of 25 or greater on the Tinnitus Functional Index (TFI) indicating the need for an intervention.

Exclusion criteria:

• Indication of significant depression (≥ 15) on the Patient Health Questionnaire (PHQ-9);

- Indications of self-harm thoughts or intent, answering affirming on Question 10 of the PHQ-9 questionnaire;
- Reporting any medical or psychiatric conditions that could interfere with the treatment;
- Reporting pulsatile, objective or unilateral tinnitus, which has not been investigated medically or tinnitus still under medical investigation; and
- Undergoing any tinnitus therapy concurrent with participation in this study.

Eligibility will be determined by a two-stage process as follows:

- An online screening questionnaire, which includes demographic information, health and mental health-related questions, and standardized outcome measures as shown in Table 1.
- A telephone interview during which the researcher will recheck eligibility, and provided the opportunity for potential participants to ask any questions related to the study. The study procedures will be explained, and motivational interviewing will be done to encourage participants to commit and engage in the intervention.
- Participants with a score of 15 or more on the PHQ-9 or indicated self-harm on question 10 will receive a phone consultation from a clinical psychologist on the research team. This call will ensure that they are under care elsewhere or necessary resources and/or referrals can be provided.

Recruitment Strategy

Recruited will involve many strategies including a television broadcast, promoting the study via tinnitus support groups in Texas and the American Tinnitus Association (ATA), and contracting the company "TrialFacts" to boost recruitment. Further recruitment strategies will involve the use of social media (e.g., Facebook and Twitter). Flyers and posters will be distributed to local communities and put up in clinic waiting rooms. Professionals such as audiologists and otolaryngologists in the state of Texas will be notified about the study and provided with leaflets to distribute to suitable patients. Those interested will be directed to the study website (www.tacklingtinnitus.org) where they can read more about the study and register their interest in study participation. Following registration, they will be invited to complete the screening questionnaire. They will be informed of their right to withdraw without penalty at any stage of the process.

Sample Size, Power and Attrition

Sample size estimation will be calculated using G*Power version 3.1.6 (Faul et al., 2007) and based on achieving a 13-point clinically meaning change between baseline and post-intervention using the primary assessment measure, the TFI. Pilot data (Beukes et al., Submitted) indicated 26 participants per group with a 1:1 allocation to achieve 80% power to detect a between-group mean standardized difference effect size of d = 0.50 (a moderate effect size). As this will be fewer than the 58 participants suggested using data from previous RCTs of this intervention, (Beukes et al., 2018) we selected 58 per group. In addition, sample size will be inflated to account for missing data, estimated to be 20% from the US phase I trial data (Beukes et al., 2021b). The aim will be thus to recruit 146 participants with 73 in each arm (calculated as 58/0.8).

Randomization

Participants meeting the inclusion criteria will be randomly assigned in the ratio of 1:1 and enrolled to either the experimental or control group using a computer-generated randomization scheduled by an independent research assistant in blocks of varying sizes after participants are pre-stratified for language (English and Spanish).

Patient Public Partnership (PPI)

A PPI will be established to include two individuals with tinnitus who had piloted the ICBT intervention, two audiologists, two researchers. Meetings will be held via video conferencing. The aim of the PPI will be to guide the study processes and input into the research strategy to boost recruitment and other elements of the study to ensure high compliance and engagement.

Intervention

The ICBT intervention content will be based on a CBT self-help program originally developed in Swedish (Andersson & Kaldo, 2004) and later adapted and translated in English (Abbott, et al., 2009). The intervention will be subsequently transformed into an 8-week interactive e-learning version suitable for a UK population (Beukes, et al., 2016) and then adapted linguistically and culturally to ensure suitability for a US population (Beukes, et al., 2020). These adaptions prioritized accessibility of the intervention, such as lowering the readability to below the recommended 6th-grade level, as more than half the US adult population have low literacy skills (Statistics, 2003). The intervention will be augmented by a module on mindfulness and more videos. The ICBT platform in the US application consisted of 22 modules with worksheets and quizzes (see Beukes et al., 2020; Beukes et al., 2021a for more details).

The intervention platform will be transferred from Sweden and housed in the US (Lamar University) to comply with the needed US data protection regulations. Prior to this feasibility trial, acceptability and functionality of this intervention for a US population will be first ensured (Manchaiah et al., 2020). Further details about the features, functionalities, and intervention components are presented in Manchaiah et al. (2020).

Both groups will received the same intervention, only the timings regarding receiving the intervention will vary. The control group will receive the experimental intervention 8 weeks after the experimental group commenced the program.

Audiology Guidance

Guidance will be provided to support participants while undertaking the intervention. This will include monitoring progress, monitoring weekly scores, providing feedback on worksheets completed, outlining the content of new modules, and answering questions.

Outcome Measures

Primary Outcome Measure

The primary outcome measure will be tinnitus severity as measured by the Tinnitus Functional Index (TFI; Meikle et al., 2012). The TFI has been translated into more than 15 languages and been validated for several populations including Chinese, Dutch, Swedish and German (Henry et al., 2016). It will be selected over other tinnitus questionnaires as it will be specifically developed to measure tinnitus severity and assess responsiveness to treatment and for comparison purposes with previous trials (e.g., Beukes et al., 2018). Meikle et al. (2012) reported that meaningful changes occur when scores are reduced by 13 points or more.

Secondary Outcome Measures

Secondary outcome measures will assess anxiety, depression, insomnia, tinnitus cognitions, hearing-related difficulties, and health-related quality of life, as shown in Table 1. To reduce the assessment load, the Tinnitus and Hearing Survey (THS; Henry, et al., 2015) will be used

to identify hearing disability and hyperacusis as it only includes 10 questions. The section on tinnitus also served as a secondary tinnitus measure. The EQ-5D-5L (Herdman, et al., 2011) will be selected to measure general health-related quality of life. All questionnaires will be used with the required permissions and agreements will be set up for those that are not freely available to use. For Spanish speakers, validated Spanish translated versions will be used. Where these will be unavailable, validated translations will be undertaken (Manchaiah, et al., 2020b).

Weekly Monitoring During the Intervention

Throughout the program, participants will be monitored weekly by means of the Tinnitus Handicap Inventory, Screening version (THI-S). The THI-S consists of a 10-item questionnaire and scores are comparable (r = .90) with the full version of the THI (Newman et al, 2008). The weekly scores will be also used to detect possible adverse effects. If scores increased by more than 10 points between two consecutive weeks, this will be noted as an adverse effect. Those indicating adverse effects will be contacted to address the identified problems. Participants will be also monitored by a newly developed Tinnitus Qualities Questionnaire (TQQ; Beukes et al., 2021a). The TQQ measures tinnitus qualities such as pitch, loudness, and the number of tones heard. The scores of TQQ can range between 0 to 100 with higher scores indicating more problematic tinnitus.

Intervention Variables

Intervention compliance will be assessed by determining retention rates and compliance in completing outcome questionnaires. Intervention engagement will be assessed by the number of logins, the number of modules read, and the number of messages sent during the intervention. Adverse effects will be monitored by 1) Direct questioning in the outcome questionnaire regarding the presence of adverse effects 2) Adverse effects written in messages or worksheets 3) An increase of 10 points or more during weekly monitoring using the THI-S questionnaire.

Questionnaire Administration

Online questionnaires will be used throughout the study. All the measures will be completed at baseline, T1 (post-intervention for experimental group), T2 (post-intervention for the control group and at two-month follow-up for the experimental group). To have a measure of the control group 2 months post intervention, participants completed further outcome measures at T3. For data analysis purposes the T3 results for the control group and those at T2 for the experimental group will be compared in order to assess the invention effect at same experimental time point for both groups (i.e., 2 months post intervention). To maximize retention, 3 electronic reminders will be sent to participants who had not completed questionnaires, on the 3 consecutive days after the release of the questionnaire. A further reminder will be sent out via email and text message. If questionnaires will be still not completed participants will be telephoned to encourage questionnaire completion. Participants will be also phoned after completing the intervention to discuss the progress they had made and share their questionnaire results.

Statistical Analysis Plan

Statistical analyses will be performed using the Statistical Package for Social Sciences (SPSS) version 26.0. All statistical tests will be 2- tailed with an alpha set to .05. To account for missing data from participants not completing the post-intervention or follow-up intervention analysis an imputation analysis will be undertaken. Missing data will be handled through multiple imputation using the *Markov Chain Monte Carlo* approach (Jakobsen et al.,

2017). For comparison, a complete case analysis will be also performed by analyzing only the completed questionnaire data without imputing missing data. As there will be substantial differences, statistical analysis using the imputed data are reported in the results section.

The primary study outcome will be a change in TFI score between the groups at postintervention (T1). A difference in scores between T1–T2 for the experimental group will be used to assess the stability of intervention effects. According to recommendations for statistical analysis of internet interventions effect sizes, linear mixed effects models, and the reliable change index will be used to assess the primary and secondary outcomes (Hesser, 2015). Changes from baseline to post-intervention will be compared within and between groups using the pre-post-test effect size (Cohen's *d*) for all primary and secondary outcomes using the observed data. Effect sizes of d = 0.20 represent small effect sizes; those of d =0.50, medium effect sizes; and those equal or greater than d = 0.80, large effect sizes (Cohen, 1992).

A Linear Mixed Model (LMM), which provides unbiased results in the presence of missing data (using all available data), will be applied to analyze the intervention effect over time for each outcome measure. An unstructured-repeated effects and identify-random effects covariance structure provided the best model fit based on the Akaike's Information Criterion (AIC). Time will be treated as a repeated and fixed effect. Restricted maximum likelihood estimation will be applied. The Type III F test sums of squares from the LMM will be calculated. As a sensitivity analysis, baseline tinnitus severity will be initially added as a covariate, but as it had no significant effect on the results it will be removed from the model.

Another model will be run to test the differences during the course of the 8 weeks intervention for the weekly outcome measures. Post hoc time comparison will be carried out in the case of significant group differences to assess at which time points these differences occurred.

In addition to statistical significant, clinical significance will also reported. A 13 point difference is recommended by the original developers of the TFI (Meikle et al, 2012) to indicate a meaningful change in scores. To handle study variability, the reliable change index (RCI) (Jacobson & Truax, 1991) is recommended as a means of calculating clinical significance for the TFI as the primary outcome. This will be calculated using the mean pretest-posttest score difference, the pretreatment standard deviation (17.49), and a test-retest reliability coefficient of 0.78, and as reported in the validation study

Sample Characteristics

Descriptive statistics including gender, age, ethnicity, race, tinnitus duration, hearing aid use, and professionals consulted, ease of computer use, veteran status, education and employment status will be used to describe the sample. The means and standard deviations will be reported for each outcome measure at each time point. Descriptive statistics will be also used to describe the sample and intervention engagement including the number of logins and modules read. A Chi square test of independence will be used to identify group differences regarding engagement and compliance rates.

Dimension	Outcome Measures	Internal consistency	Range of scores	Levels of significance	Timeframe : T0 (baseline)	Timeframe: T1	Timeframe: T2	Timefra me: T3
Explanation						Post- intervention for the experimental group; post weekly monitoring for the control group	2 month follow-up for experiment al group, postinterve ntion for the control group	2 month follow-up for the control group
Tinnitus distress	Tinnitus Functional Index (TFI; Meikle et al, 2012)	.97	0-100 A reduction of scores indicates improvement	>25= mild (no need for intervention) 26-50= significant (possible need for intervention) 50+ =severe (need for a more intense	Both groups x	Both groups	Both groups	Control group only x
Generalized Anxiety	Generalized Anxiety Disorder (GAD-7, Spitzer, Kroenke, Williams, et al., 2006)	.89	0-21 A reduction of scores indicates improvement	intervention) 0-4= minimal anxiety 5-9= mild anxiety 10-14= moderate anxiety 5-21= severe anxiety	X	x	x	x

Table 1. Study outcome measures used pre-intervention, post-intervention and at 2-months follow-up

Depression	Patient Health Questionnai re (PHQ-9; Spitzer, Kroenke	.83	0-27 A reduction of scores indicates improvement	5-9=mild depression 10-14=moderate 15-19=moderately severe 20-18= severe depression	x	X	X	x
	Williams, 1999)							
Insomnia	Insomnia Severity Index (ISI; Bastien, Vallières, & Morin, 2001)	.74	0-28 A reduction of scores indicates improvement	0-7 = Not clinically signi 8-14 = Subthreshold inso 15-21 = Clinical insomnia (moderate severity) 22-28 = Clinical insomnia (severe degree)	X	Х	X	X
Tinnitus Cognitions	Tinnitus Cognitions Questionnai re (TCQ; Wilson & Henry, 1998)	.91	0-104 A reduction of scores indicates improvement	Higher scores indicate a greater tendency to engage in negative cognitions in response to tinnitus	X	Х	X	X
Health-related quality of life	EQ-5D-5L (Herdman, et al., 2011)	.785	0-15 A reduction of scores indicates improvement	Measures 5 dimensions: mobility, self-care, usual activities, pain/discomfort, and anxiety/ depression	X	X	X	x
Health-related quality of life	EQ-5D-5L Visual Analogue Scale	.785	0-100 Higher scores indicates improved health	VAS for overall health.	X	X	X	X

	(VAS) (Herdman,							
	et al., 2011)							
Short measure	Tinnitus	.8694	Subscale for		X	Х	Х	Х
for tinnitus,	and Hearing		Tinnitus: 0-16					
hearing	Survey		Hearing: 0-16					
disability and	(THS;		Sound tolerance:					
hyperacusis	Henry, et		0-8					
	al., 2015)							
Weekly monitoring								
Screening of	Tinnitus	.93	0-40	>6 tinnitus handicap		Weekly while		
tinnitus severity	Handicap		A reduction of	-		undertaking		
	Inventory-		scores indicates			the 8-week		
	Screening		improvement			intervention		
	(THI-S)							
	(Newman,							
	Sandridge,							
	& Bolek,							
	2008)							
Tinnitus percept	Tinnitus	Not	0-100	Designed to determine		Weekly while		
	Qualities	assessed	A reduction of	whether tinnitus qualities		undertaking		
	Questionnai		scores indicates	such as loudness, pitch,		the 8-week		
	re		improvement	the number of tones		intervention		
	(TQQ;			heard and so forth				
	Beukes,			improves while				
	Andersson,			undertaking an				
	Manchaiah,			intervention. Higher				
	& Kaldo,			scores indicate more				
	2021a)			bothersome aspects of				
	,			tinnitus are present.				

T0= preintervention; T1=8 weeks after the experimental group started the intervention, prior to the control group starting; T2=8 weeks after the experimental group complete the intervention and at post-intervention for the control group.

Bibiliography

- Abbott, J. M., Kaldo, V., Klein, B., Austin, D., Hamilton, C., Piterman, L., & Andersson, G. (2009). A cluster randomised controlled trial of an Internet-based intervention program for tinnitus distress in an industrial setting. *Cognitive Behaviour Therapy*, 38(3), 162-173. http://doi:10.1080/16506070902763174
- Andersson, G. (2002). Psychological aspects of tinnitus and the application of cognitive behavioral therapy. *Clinical Psychology Review*, 22(7), 977–990. https://doi.org/10.1016/S0272-7358(01)00124-6
- Andersson, G., & Kaldo, V. (2004). Internet-based cognitive behavioral therapy for tinnitus. *Journal of Clinical Psychology*, 60(2), 171-178. https://doi.org/10.1002/jclp.10243

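### The self-harm exclusion and one trigger for the psychologist call cite a Question 10 of the PHQ-9 that the plan does not define and that does not fit its own 0-27 scoring

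*Combined protocol and SAP*

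**What the plan says.** Three places in the combined protocol and SAP bear on this.

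- **Exclusion criteria (Study Population).** One criterion is the total score: "Indication of significant depression (≥ 15) on the Patient Health Questionnaire (PHQ-9"). The next is a separate, item-level criterion: "Indications of self-harm thoughts or intent, answering affirming on Question 10 of the PHQ-9 questionnaire".
- **Study eligibility, two-stage process.** The call has two alternative triggers: "Participants with a score of 15 or more on the PHQ-9 or indicated self-harm on question 10 will receive a phone consultation". The caller is a clinical psychologist on the team, and the stated purpose is to make sure that the person is under care or is given resources or referrals.
- **Table 1, Depression row.** The instrument is named PHQ-9, and its scoring is given as "0-27 A reduction of scores indicates improvement".

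The first stage of screening is described as "An online screening questionnaire, which includes demographic information, health and mental health-related questions, and standardized outcome measures as shown in Table 1". The second stage is a telephone interview in which a researcher checks eligibility again. The inclusion criteria admit people who use English or Spanish, and the plan calls for validated Spanish versions of the questionnaires.

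The plan contains no list of PHQ-9 items, no item wording, no points per item, and no mention of a supplementary or unscored question.

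**The concern.** The item-level rule is the only self-harm criterion in the plan, and it carries two consequences: exclusion and a call from a psychologist. Both are tied to a question number that does not fit the instrument as Table 1 scores it. The number appears in two separate sentences, so it is unlikely to come from the conversion of the PDF.

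The total-score rule is an independent route to the same two consequences, but only from 15 upwards. For someone who reports self-harm thoughts at a lower total, the exclusion and the call both rest on the item reference. If the screening form were set up from the number and not from the content, such a person could be missed, and someone who affirmed a different question could be excluded without cause. Whether that happened depends on how the form was built, which the plan does not describe.

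The matter concerns participant safety and who enters the trial. It does not touch the sample size, the alpha level or the analysis model.

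**Working it through.** **Inputs.** From the documents: the name PHQ-9 and the range 0-27 (Table 1), the threshold of 15 or more (Exclusion criteria, and the rule for the call), and the reference to Question 10 (the same two places). Assumed, because the plan does not state it: items carry equal whole-number scores, and the 9 in the name is the number of items.

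**Step 1: reproduce the stated range.** Maximum score = number of scored items x maximum points per item.

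- Nine items scored 0-3: 9 x 3 = 27. This reproduces Table 1.
- Ten items scored 0-3: 10 x 3 = 30. This does not.
- Ten equally scored items with a maximum of 27: 27 / 10 = 2.7 points each, which is not a whole number.

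**Step 2: how far the range alone goes.** The item counts that divide 27 evenly are 1, 3, 9 and 27. The range therefore rules out ten equally scored items, but on its own it does not single out nine. The name of the instrument does that. Nine items is thus an inference from name and range together; Table 1 prints no item count.

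**Step 3: where Question 10 falls.** With nine scored items, a tenth question is outside the set that makes up the 0-27 score. The arithmetic cannot say what a tenth, unscored question would ask. Nor can it exclude that the number is the item's position in the longer online questionnaire.

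**Step 4: does the total-score rule cover the gap?** Suppose the self-harm item is one of the nine and is answered s = 1, 2 or 3. The other eight items can add up to 8 x 3 = 24. The total stays below 15 as long as those eight add up to no more than 14 - s:

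| Self-harm answer s | Largest sum of the other eight items with total below 15 | Totals not caught by the 15-or-more rule |
|---|---|---|
| 1 | 13 | 1 to 14 |
| 2 | 12 | 2 to 14 |
| 3 | 11 | 3 to 14 |

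So even the strongest self-harm answer can go with a total anywhere from 3 to 14. If the self-harm question is instead unscored, it adds nothing to the total, and the uncovered totals are 0 to 14. In both cases the item-level trigger has to work by itself below 15.

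**The case against.** The strongest reply is that this is a slip in a number and nothing more. Both rules name self-harm in words, so anyone applying them knows what to look for, and a mismatched item should be noticed. The PHQ-9 is given inside a longer online questionnaire, where its items may carry other numbers. The telephone interview is a second check on eligibility, another criterion excludes psychiatric conditions that could interfere with treatment, and a total of 15 or more triggers exclusion and the call by itself. The plan describes no automated flag.

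Much of this stands. A reader might infer that the screen points at a question outside the instrument, that a tenth question cannot be the self-harm item, or that the rule as run would catch nobody below 15. The documents support none of these. They give no item wording, they show nothing of the form as built, and the rules name the content beside the number. A mislabelled number with a correctly run screen explains the text equally well.

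The reply does not make the reference sound. Nothing in the plan says which of these explanations applies. The telephone interview is given no self-harm criterion of its own, so what it checks again is the rule that cites Question 10. The other safeguards do not replace an item-level trigger at totals below 15.

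**Conclusion.** The concern holds as an inconsistency within the plan. The self-harm exclusion, and one of the two triggers for the psychologist call, cite a Question 10 that falls outside the scored item set implied by Table 1 and is not defined anywhere. This rests on reading the PHQ-9 as nine items scored 0-3, an inference from its name and the 0-27 range.

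Its size can be stated only as a range of scores: a self-harm response with a total of 1 to 14 (0 to 14 if the question is unscored) depends wholly on the item reference. The documents give no frequency for such responses, so no number of people can be derived. They also do not show that anyone was wrongly enrolled, wrongly excluded or left without a call.

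The point should be corrected even so, because the undefined reference sits in an operative safety rule and the correction is cheap.

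**What to change.** Reconcile the exclusion criterion, the rule for the psychologist call and the PHQ-9 row of Table 1 with the English and Spanish forms as administered. Then:

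1. In both rules, identify the trigger item by its wording and by its number on those forms. If the form has an unscored extra question, say so in Table 1.
2. Confirm that the exclusion trigger and the call trigger both read that item, in each language.
3. If either did not, query the stored screening responses for people affected and record the result.

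The clinical rule and the threshold of 15 are not at issue and do not change. The cost is a wording edit in two places, possibly a note to Table 1, and one check of the forms; a single query of stored data is needed only if that check fails.

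### The plan does not say whether its PHQ-9 alert response, written for eligibility, applies to the PHQ-9 forms at T1, T2 and T3, and its adverse-effect routes do not use PHQ-9 answers

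*Combined protocol and SAP*

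**What the plan says.** Under Study eligibility, two exclusion criteria rest on the PHQ-9. One is a score of 15 or more. The other reads: "Indications of self-harm thoughts or intent, answering affirming on Question 10 of the PHQ-9 questionnaire". The section then says "Eligibility will be determined by a two-stage process as follows", and the list that follows ends with the response to a positive finding: the person "will receive a phone consultation from a clinical psychologist on the research team". Its purpose is also given: "This call will ensure that they are under care elsewhere or necessary resources and/or referrals can be provided". The next heading is Recruitment Strategy.

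Questionnaire Administration repeats the full set of questionnaires after enrolment, online: "All the measures will be completed at baseline, T1 (post-intervention for experimental group), T2". Controls complete a further set at T3. The depression row of Table 1 marks the PHQ-9 at T0, T1, T2 and T3.

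Intervention Variables lists three ways of detecting adverse effects: a direct question within the outcome questionnaire, remarks in messages or worksheets, and a rise on the weekly THI-S. Weekly Monitoring During the Intervention adds that people who indicate adverse effects are contacted. Questionnaire Administration also has a routine call: "Participants will be also phoned after completing the intervention to discuss the progress they had made and share their questionnaire results".

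**The concern.** The protocol treats these PHQ-9 findings as serious enough to keep a person out of the trial and to have a psychologist phone them. After enrolment the same answers arrive on the same form, with no stated reader, timing or response. A control who enrols with a score of 14 and reaches 15 or more at T1 goes on to ICBT with no stated check. The same score at screening would have meant exclusion and a psychologist's call.

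Two things are at stake. The first is participant safety. The second is what the trial can say about harm: a move into the trial's own exclusion range is not defined as an adverse effect, so the adverse-effect count by arm could omit a harm that the protocol itself names.

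**Working it through.** The plan states no figure to reproduce. The check compares each post-baseline PHQ-9 form with the provisions that might act on it.

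**Number of forms.** Sample Size, Power and Attrition plans 73 per arm. Table 1 and Questionnaire Administration give two post-baseline assessments in the experimental arm (T1, T2) and three in controls (T1, T2, T3).

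- Experimental: 73 × 2 = 146
- Control: 73 × 3 = 219
- Total: 146 + 219 = 365

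These are planned forms before any missing data, and they are forms rather than people, since one person may contribute up to three.

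**The psychologist's call.** It is the last item in the list on determining eligibility, and its thresholds match the two exclusion criteria. Placement and purpose point to screening. No other section ties a response to a PHQ-9 answer.

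**The adverse-effect routes.** None of the three uses a PHQ-9 score or the self-harm item.

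- The direct question depends on the participant regarding the problem as an adverse effect. A control at T1 has had no ICBT to which to attribute one.
- Guidance, including feedback on worksheets, is described as support during the intervention.
- The THI-S measures tinnitus severity, and Table 1 places it weekly during the 8-week intervention. The Randomization text also has controls monitored weekly in the first phase.
- For the experimental arm at T2 and controls at T3, two months after ICBT, the direct question is the only route that clearly still operates.

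**The routine call.** It follows completion of the intervention, so it can be matched to two sets of forms.

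| Forms | Number | Follows completion of ICBT in that arm? |
|---|---|---|
| Experimental, T1 | 73 | Yes |
| Control, T2 | 73 | Yes |
| Control, T1 | 73 | No (ICBT not yet started) |
| Experimental, T2 | 73 | No (two-month follow-up) |
| Control, T3 | 73 | No (two-month follow-up) |

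The call could reach 73 + 73 = 146 forms if everyone completes the intervention and returns the form. That leaves 365 − 146 = 219 outside it. Even for the 146, the call has no stated timing, is not prompted by an alert, and is not described as a psychologist's call.

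**The case against.** A reader might infer that self-harm reported after enrolment would lead to no action. The documents do not support that, for three reasons.

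- People who indicate adverse effects are contacted, and self-harm disclosed in a message, a worksheet or the direct question could come in that way. The contact sentence sits in the weekly-monitoring section, so its reach to every route is arguable, but it is there.
- The routine call shares questionnaire results, so someone on the team looks at results around the end of each arm's intervention.
- The screening sentence has no explicit time limit: "Participants with a score of 15 or more on the PHQ-9 or indicated self-harm on question 10 will receive a phone consultation". It could be read as covering later forms, and it is a third item under a process described as having two stages. Consent pages are not part of the text reviewed, so a procedure described there would not be visible.

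These points stand, and they limit the finding to what the plan states. They do not close the gap. The contact step depends on routes that omit PHQ-9 answers, the routine call misses three of the five sets of forms, and the wider reading of the screening sentence has to be guessed against its placement.

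It can also be said that depression is already a secondary outcome, with a mixed model, effect sizes, and means and standard deviations at each time point. That is so, and average worsening would be visible. An arm's mean can improve, however, while some members cross into the exclusion range, and the self-harm item is not reported separately. The individual count is what is missing.

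Finally, the documents give no rate of PHQ-9 alerts after baseline. Any forecast of their number would rest on an assumed rate, so none is offered.

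**Conclusion.** The concern holds as a gap in the stated plan, and it should be corrected. The only response tied to the PHQ-9 thresholds is placed in the eligibility process. The plan does not state that it applies to any of the 365 planned post-baseline forms. No adverse-effect route uses PHQ-9 answers, and 219 of the 365 forms also fall outside the routine call as written.

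Followed literally, the plan gives weaker protection after enrolment than at screening, and an adverse-effect count that can leave out new significant depression or self-harm. The form counts assume 73 per arm and full return. The textual finding does not depend on them. The sponsor may have intended the response to continue after enrolment; the documents do not settle this.

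**What to change.** Reconcile the last item of the eligibility list with Intervention Variables, Questionnaire Administration and Table 1, so that the protocol says whether and how the existing PHQ-9 response operates at T1, T2 and T3 in both arms. The clinical response is for the investigators to set.

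In the harms reporting, count by arm and time point the participants who newly meet either PHQ-9 exclusion criterion after baseline, giving the number of returned forms as the denominator. Compare the arms at T1, the one post-baseline assessment before controls start ICBT. Because the eligibility criteria exclude anyone who meets either criterion at entry, each participant's first such finding after baseline is a new one.

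The cost is protocol wording, a small amount of extra review and reporting from a form already collected online, and possibly a few more calls by the psychologist already on the team.
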